4.3.2 Safety and Tolerability

NT-814 has been well tolerated both after single and repeat doses. All reported adverse events (AE) have been transient and mild or moderate in severity; no treatment-related serious adverse events (SAE) have been observed. One subject in the opiate-use disorder study died after completing the study from an unrelated drug overdose. Non-serious AEs considered related to treatment with NT-814 are headache, diarrhea and somnolence.

No treatment-related effects on electrocardiogram (ECG) parameters, vital signs or routine safety laboratory testing have been observed. Extended continuous Holter ECG monitoring in the RELENT-1 study did not identify any treatment-related effect on heart rhythm.

Further information on the pre-clinical and clinical studies undertaken with NT-814 can be found in the current version of the Investigator's Brochure (IB)³³.

4.4 Study Design Considerations

This is a standard study design for assessing the effect of different doses on the serum concentrations of various hormones. It is sufficient for just the subject to be blinded to treatment as there are no subjective efficacy elements being measured in the study but blinding subjects to treatment potentially reduces bias in the reporting of safety findings. The doses proposed in this study are currently being studied in women with hot-flashes associated with the menopause. The proposed duration of treatment and number of subjects per treatment arm are considered sufficient to adequately assess the effect of NT-814 on the hormones under study.

4.5 Risks and Risk Mitigation

4.5.1 Risks to Study Subjects

As NT-814 is still in the early stages of development and its effects on the developing fetus or neonate have not been fully evaluated, pregnant or breast-feeding women must not be given NT-814. NT-814 was not genotoxic. At a dose of 100 mg/kg/day there were increased pre- and post-implantation embryo losses, reduced litter size and reduced embryo weights in fertility studies in rats. However, there was no evidence of fetal abnormalities in either rats or rabbits and there was no evidence of embryofetal toxicity in the rat at doses up to 100 mg/kg/day or in the rabbit at doses up to 140 mg/kg/day.

Subjects must be using non-hormonal birth control. Accordingly, whilst ‘highly effective’ birth control (one with a failure rate less than 1% per annum) is desirable, it is considered that two “acceptable” methods of birth control, one of which must be a barrier method with spermicide, is also appropriate for this study³⁴. Acceptable methods of contraception are listed in [Section 8.8.2](#). Hormonal contraception by any route (including a progestin-releasing intrauterine system, IUS) is not acceptable for this study since it is likely to affect the pharmacodynamic endpoints of the study. Subjects who have undergone bilateral oophorectomy will be excluded since this will also affect the pharmacodynamic endpoints, and subjects who have undergone hysterectomy will be excluded because of the difficulty in recognizing the first day of menstruation in each cycle.

Subjects who are allergic to NT-814 or any of the excipients in the formulation will be excluded.

Full lists of subject inclusion and exclusion criteria are provided in [Sections 7.2](#).

A study of photochemical properties showed that NT-814 absorbs photons in the visible part of the light spectrum and there was a positive finding in an *in vitro* phototoxicity study. The relevance of these findings is unclear. Although recommended by regulatory guidelines, the *in vitro* study has a high false-positive rate and, despite subjects in clinical studies not being required to take precautions with respect to sunlight, there have been no adverse events consistent with clinical phototoxicity. Investigators and subjects are advised to be vigilant to the occurrence of sunburn-like skin reactions and to avoid direct exposure to strong sunlight should this occur.

In general, treatment-with NT-814 has been well-tolerated in clinical studies. However, attention is drawn to the following safety information.

Several subjects participating in phase 1 studies with NT-814 were noted to have cardiac arrhythmias coincident with their participation in the studies. However, there were no findings in the pre-clinical safety studies that would suggest that NT-814 is pro-arrhythmic, and extensive Holter monitoring in the RELENT-1 study did not identify any difference between placebo and NT-814 in the incidence of arrhythmias. Nonetheless, subjects participating in studies should undergo periodic ECG evaluation, either as required by the protocol or indicated clinically.

Mild somnolence has been reported at a higher incidence in subjects receiving higher doses of NT-814. Subjects who experience somnolence should avoid driving or use of machinery.

No serious or severe adverse reactions are considered expected with NT-814. Expected adverse reactions comprise moderate headache, mild somnolence, and mild diarrhea.

Another NK₁ antagonist has recently been reported to be linked with clinically significant elevations in liver enzymes. Small (not clinically significant) rises in LFTs in subjects taking NT-814 have been

reported in the RELENT-1 study but at a lower frequency than in subjects taking placebo in that study. A subject in the ongoing (and still blinded) vasomotor symptom study was withdrawn from treatment because of elevated transaminases. Subjects participating in studies should have their LFTs monitored regularly for any unexpected rises.

4.5.2 Potential for Drug-Drug Interaction

Plasma protein binding of NT-814 was very high (greater than 99.5% in all species tested).

In vivo (rat and monkey), elimination of NT-814 was mainly by metabolism. The predominant human metabolic pathway appears to be oxidation by cytochrome P450 (CYP) 3A4. Based on a clinical interaction study with midazolam, NT-814 is also a weak inhibitor of CYP3A4.

In vitro data indicate that NT-814 is a substrate and weak inhibitor of human P-glycoprotein (P-gp). It is also a moderate inhibitor of human organic anion transporting polypeptide 1B1 and a weak inhibitor of human breast cancer resistance protein. Preliminary data from a human clinical interaction study with itraconazole indicates that NT-814 is a moderately sensitive substrate of CYP3A4 and/or P-gp.

In this study, subjects will be excluded if they are taking, or are likely to need to take, non-study medication other than low doses of paracetamol (acetaminophen) (see [Section 8.8.1](#)). The potential risk of drug-drug interaction will be taken into account in selecting concomitant medication to treat an emergent adverse event. If concomitant medication needed to treat AEs is likely to be associated with increased risk to the subject or to reduce the likelihood of achieving the study objectives, the subject should discontinue dosing with study medication and/or be withdrawn from the study (see [Section 7.4](#)).

5 STUDY OBJECTIVES AND CORRESPONDING ENDPOINTS

The study objectives and corresponding endpoints/study outcomes are presented in [Table 5-1](#).

Table 5-1 Objectives and Corresponding Endpoints/Study Outcomes

Objectives	Endpoints/Study Outcomes
Primary	
To determine the effects of NT-814 given at doses of 40 mg, 80 mg, 120 mg, and 160 mg once daily for approximately 21 days on GnRH pathway hormones in healthy female subjects	
 • Change from baseline in serum LH, FSH, estradiol and progesterone over a full menstrual cycle
Secondary	
To evaluate the safety of NT-814	
 • 12-lead ECGs: abnormalities; change from baseline in quantitative parameters (RR interval, PR interval, QRS duration, absolute QT interval and QTcF) • Change from baseline in clinical laboratory assessments (hematology, biochemistry) • Change from baseline in vital signs (BP, pulse rate, weight) • Nature and severity of TEAE; withdrawals due to TEAE
Exploratory	
To evaluate the pharmacokinetic-pharmacodynamic (PK-PD) relationship of NT-814	
 • NT-814 plasma concentration levels concurrent with serum LH, FSH, estradiol and progesterone during Cycle 2
To evaluate the effect of NT-814 on menstrual cycle length	
 • Change from baseline (Cycle 1) in the length of the menstrual cycle

6 STUDY DESIGN

The study uses a randomized, single-blind, placebo-controlled design. The study will consist of two cohorts, with the second cohort being optional depending on the pharmacodynamic (hormonal) response observed in Cohort 1.

Cohort 1 will consist of 32 subjects randomized to receive NT-814 40mg, 80mg, 120mg or placebo once daily in parallel groups, 8 subjects in each group. After Cohort 1 complete Cycle 2, the pharmacodynamic data will be assessed by a team comprising of the Sponsor medical representative, Sponsor medical expert, Investigator and statistician. If a maximal response (estradiol reduction) is not observed at the lower doses the higher dose of 160 mg dose will be assessed. A maximal response will be considered as having been achieved if the response observed at 120 mg is not meaningfully greater than that observed at 80 mg. In the case that any subjects in Cohort 1 withdraw or are withdrawn from the study prior to completion of Cycle 2 they will be replaced at the discretion of the Sponsor.

If the 160mg dose is to be assessed an additional Cohort 2 will be enrolled – consisting of 10 subjects randomized to receive either NT-814 160mg (8 subjects) or placebo (2 subjects).

Subjects will participate in the study during two consecutive menstrual cycles.

After obtaining written informed consent, each subject will undergo screening procedures within 21 days before the anticipated start of the baseline assessment cycle (Cycle 1).

Eligible subjects will first attend the study unit on the morning of either Day 3 or 4 of Cycle 1 (where Day 1 is the first day of menstruation) for the start of the baseline assessment cycle. Blood samples will be collected for measurement of hormones (estradiol, progesterone, LH, and FSH).

Subjects will return to the study unit for a further three out-patient visits on the mornings of Day 9 or 10, Day 15 or 16, and Day 21 or 22. Blood samples for serum hormones will be collected at each visit. Samples for serum hormone assessment must be taken at the same time of day on all days (± 1 hr).

At the clinic visit on Day 21 or 22, subjects will additionally have safety assessments performed.

Subjects will return to the study unit in the morning of either the day of or the day following (or, in exceptional circumstances, 2 days following) the first day of their next menstrual cycle (the first day of bleeding; Cycle 2) and, after completion of baseline safety assessments, will be randomized to study treatment; they will then receive their first dose of study medication. They will attend the study unit daily in the morning for up to 20 further days to receive their study medication (so a total of up to 21 days dosing) with the last dose to be taken on the day prior to the Day 21 or 22 visit.

Additionally, on Day 3 or 4, Day 9 or 10, Day 15 or 16, and Day 21 or 22, blood samples for serum hormones will be collected and a single sample for measurement of plasma levels of NT-814 will also be collected. Blood samples for serum hormones (and PK) must be taken at the same time of day as the hormone samples were taken in Cycle 1 (± 1 hr).

The serum hormone sampling days relative to Day 1 of Cycle 2 will match the days samples were taken in Cycle 1 (relative to Day 1 of Cycle 1) within each subject (e.g. if the subject attended the clinic on Day 4 in Cycle 1, the hormone sample must be taken on Day 4 in Cycle 2; if they attended on Day 9 in Cycle 1 the hormone sample must be taken on Day 9 in Cycle 2, and so on).

If the subject unexpectedly cannot attend on Days 1-3 of their next menstrual cycle they can remain in the study and Cycle 2 will be scheduled for their next menstrual cycle. Clinic staff should keep in close

[figure not shown]
contact with the subject and instruct them to attend the clinic on Day 1 or 2 (or 3 in exceptional circumstances) of their subsequent menstrual cycle. Because of the delay between randomization and the previous safety laboratory assessments (performed Day 21/22 Cycle 1), these subjects will need to attend the clinic on Day 1 or 2 early enough to ensure that safety laboratory samples can be taken, and the results assessed prior to randomization and dosing.

Safety will be monitored throughout the study with routine safety assessments (AE recording; vital signs; 12-lead ECG; clinical laboratory tests). A physical examination will be conducted at screen and follow-up. Additional safety assessments will be done at any time as considered appropriate by the Investigator. Additional safety assessments not specified in the protocol may be performed as required by Quotient Sciences Standard Operating Procedures, but these will not be entered into the eCRF. Any abnormal assessments observed during non-protocol required safety assessments will be recorded as AEs if appropriate and the corresponding abnormal assessment entered as an unscheduled assessment in the eCRF.

Subjects will have a final outpatient follow-up visit two weeks following the final dose of study medication. At this visit the subject will be asked when their next menstrual cycle started (the cycle after the completion of dosing).

An overview of the study is shown in [Figure 6-1](#).

Figure 6-1: Study Schematic

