Fraser et al showed that 21 days' treatment in regularly cycling women with ESN364 resulted in decreases in LH but not FSH. This led to decreases in estradiol and progesterone causing delay in ovulation, decreased endometrial thickening, slowed follicular maturation and an extended cycle³².

Taken together, the evidence suggests that NK antagonists might selectively reduce LH levels but not FSH due to modulation of the GnRH pulse frequency. This reduces level of ovarian hormones but not to a level that would lead to adverse events associated with post-menopausal hormone levels. Along with an acceptable safety profile, this raises the potential of NK antagonists to be used in the treatment of uterine fibroids and endometriosis.

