9 STUDY ASSESSMENTS AND PROCEDURES

Please see [Table 9-1](#) for the complete schedule of assessments. [Section 9.6](#) summarizes the order of procedures when more than one activity is scheduled for the same time point and permissible time windows.

Table 9-1 Schedule of Events

Day	Screening	Cycle 1					Cycle 2					Follow-up
	-21 ^a	1	3/4	9/10	15/16	21/22	1/2	3/4	9/10	15/16	21/22	35-38
Clinic visit (out-patient)	X		X	X	X	X	X					X ^e
Informed consent	X ^b											
Menstrual flow starts		X					X ^l					
Record dates of start of menstruation		X										X
Medical History	X											
Physical examination	X											X
Vital signs ^c	X					X	X ^f	X ^h	X ^h	X ^h	X	X
Oral or aural body temperature	X						X ^f					X
12-lead ECG	X					X	X ^f	X ^h	X ^h	X ^h	X	X
Weight	X					X	X					X
Serology ^d	X											
Drugs of abuse screen	X					X	X ^f					
Hematology and Clinical Chemistry	X					X	X		X		X	X
Serum pregnancy test	X					X						X
Urine pregnancy test							X ^f					
Sample for PD hormone assessment			X	X	X	X		X ^{h,i}	X ^{h,i}	X ^{h,i}	X ⁱ	
Sample for PK								X ^{h,j}	X ^{h,j}	X ^{h,j}	X ^j	
Randomization						X						
NT-814/placebo once daily							X					X ^g
Adverse Event / con med reporting ^k	X											X

- a Screening to be scheduled within 21 days of the anticipated start of the next menstrual cycle. This period can be extended if the menstrual period starts later than anticipated.
- b Informed consent can be obtained prior to the screening visit. The screening period starts from the date of the screening procedures, not from the date of consent.
- c Vital signs: systolic and diastolic blood pressure, pulse
- d Hepatitis B surface antigen, hepatitis B core antibody, hepatitis C antibody, human immunodeficiency virus
- e Daily clinic visits in the morning, starting on Day 1 or 2 of Cycle 2 and ending on Day 21/22.
- f Performed prior to the first dose
- g Doses administered in the morning, in the clinic ~1-2 hours after breakfast; starting on Day 1 or 2 of Cycle 2; last dose will be day prior to clinic visit on Day 21/22. Doses to be administered at the same time each day (±1hr).
- h Prior to administration of dose on the days shown
- i PD sample days must be the same relative to Day 1 on both Cycles 1 and 2
- j PK samples taken on same day/time as PD samples in Cycle 2
- k AEs and concomitant medication to be reported from the start of screening
- l Requires visual verification

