11.3 Data Analysis and Reporting

Full details of the proposed statistical and pharmacodynamic analyses will be documented in the Reporting and Analysis Plan (RAP), which will be written following finalization of the protocol and finalized before locking the database.

Where applicable, values will be converted from local to Système International (SI) units for reporting; both original and converted values will be listed.

PD and safety data will be presented by means of descriptive statistics and figures, as appropriate, by treatment arm and time point. All data will be listed.

Summary statistics will be based primarily on non-missing values. Full details on the handling of missing values will be defined in the RAP.

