11.3.3 Pharmacodynamic analysis methodology

The pharmacodynamic data (i.e. LH, FSH, estradiol and progesterone) in Cycle 2 will be assessed versus baseline (Cycle 1), and descriptive statistics for change from baseline will be produced, where applicable.

The changes from baseline will be analyzed using a fixed effects model with treatment as a fixed effect and the corresponding baseline value as a covariate. The adjusted arithmetic means from the model for the changes from baseline including 95% confidence interval (CI) will be presented for each treatment. In addition, the following comparisons will be performed and the difference in the adjusted arithmetic means and 90% CI will be presented:

- each dose level of NT-814 vs placebo

This analysis will be performed for each day separately (i.e. Days 3/4, 9/10, 15/16 and 21/22). A repeated measures analysis may be used if considered appropriate.

For the exploratory analysis of the change in menstrual cycle length, the length of Cycle 2 will be assessed versus baseline (length of Cycle 1), and descriptive statistics for change from baseline will be produced, where applicable.

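### Exploratory cycle-length endpoint: the end of Cycle 2 is recorded only if menses start by the follow-up visit, so a Cycle 2 longer than 34 to 37 days has no end date

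*Protocol*

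**What the plan says.** Table 5-1 (Section 5) lists as an exploratory endpoint "Change from baseline (Cycle 1) in the length of the menstrual cycle". Section 11.3.3 says that "the length of Cycle 2 will be assessed versus baseline (length of Cycle 1), and descriptive statistics for change from baseline will be produced".

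Cycle 2 ends when the next menses begin. Section 6 provides for a "final outpatient follow-up visit two weeks following the final dose of study medication" and then states: "At this visit the subject will be asked when their next menstrual cycle started (the cycle after the completion of dosing". In Table 9-1 the row "Record dates of start of menstruation" has its last entry in the Follow-up column, which is headed Day 35-38. Dosing stops before the last hormone visit, "with the last dose to be taken on the day prior to the Day 21 or 22 visit" (Section 6).

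Two further passages bear on the point. Section 4.1 reports that 21 days of another NK3 antagonist in regularly cycling women led, among other effects, to "slowed follicular maturation and an extended cycle". Section 11.3 says "Summary statistics will be based primarily on non-missing values" and leaves the details of missing-value handling to the Reporting and Analysis Plan (RAP).

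**The concern.** The follow-up visit is timed from the last dose, as suits a safety visit, but it is also the last occasion on which the end of Cycle 2 can be recorded. A woman who has not bled by then has no Cycle 2 length. Her cycle is known only to be at least as long as the visit-day number.

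Whether the date is missing depends on the outcome itself: only long cycles lose their end date. On the evidence that the protocol cites for the class, lengthening is the effect to be looked for, so the loss would fall mainly on the active arms. A summary of recorded cycles would then understate any prolongation. The RAP can decide how to treat open cycles, but it cannot supply dates that were never collected. The data-collection limit is set by the protocol.

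**Working it through.** **1. Visit day (Sections 6 and 9).** The last dose is one day before the Day 21 or 22 visit, so on Day 20 or 21. Adding 14 days gives Day 34 or 35. Table 9-1 gives Day 35-38. The two overlap only at Day 35.

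**2. Longest Cycle 2 with an end date.** A cycle of length L ends when menses start on Day L + 1. The date is available at a visit on Day f only if L + 1 ≤ f, so L ≤ f − 1.
- Section 6, read exactly: f = 34 or 35, so L ≤ 33 or 34.
- Table 9-1: f = 35, 36, 37 or 38, so L ≤ 34, 35, 36 or 37.

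If menses have not started by Day f, then L ≥ f. These limits need no assumption beyond completed dosing. If a subject stops early, two weeks after the last dose comes sooner and the limit is shorter.

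**3. Share of open cycles.** The protocol gives no mean, SD or expected extension; inclusion criterion 2 asks only for roughly monthly periods. Assumed here: length in whole days from a normal distribution, untreated mean m = 28 or 30, SD s = 2.5, 3 or 4 (six scenarios), extension δ. Then

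P(open at Day f) = 1 − Φ((f − 0.5 − m − δ)/s).

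For δ = 5:
- f = 35, lowest (m = 28, s = 2.5): 1 − Φ(1.5/2.5) = 0.274
- f = 35, highest (m = 30, s = 2.5): 1 − Φ(−0.5/2.5) = 0.579
- f = 38, lowest (m = 28, s = 2.5): 1 − Φ(4.5/2.5) = 0.036
- f = 38, highest (m = 30, s = 4): 1 − Φ(2.5/4) = 0.266

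In an arm of 8 that is 2.2 to 4.6 women at Day 35 and 0.3 to 2.1 at Day 38.

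| Extension | Open at Day 35 | Open at Day 38 |
|---|---|---|
| 0 days | 0-13% | 0-3% |
| 3 days | 8-35% | 0-13% |
| 5 days | 27-58% | 4-27% |

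**4. Effect on the endpoint.** The endpoint is each woman's Cycle 2 minus Cycle 1. Cycle 1 closes when Cycle 2 opens, so only Cycle 2 is cut off. With correlation ρ between a woman's two cycles and joint normality, the shortfall in mean change is (1 − ρ) times the shortfall in mean Cycle 2 length. For δ = 5, the difference in mean change between treated and untreated women with recorded cycles is:

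| ρ | Day 35 | Day 38 |
|---|---|---|
| 0 | 2.4-3.9 | 3.5-4.8 |
| 0.5 | 3.7-4.4 | 4.2-4.9 |
| 0.7 | 4.2-4.7 | 4.5-4.9 |

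Example (m = 30, s = 4, f = 35): at ρ = 0 the difference is 2.44, a shortfall of 5 − 2.44 = 2.56. At ρ = 0.5 the shortfall is 0.5 × 2.56 = 1.28, so the difference is 3.72. The values of ρ are assumed; the protocol gives none.

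**5. Longer collection.** Thirty days after a last dose on Day 20 or 21 is Day 50 or 51. Even with δ = 10 and the least favourable scenario (m = 30, s = 4), the share open at Day 50 is 1 − Φ(9.5/4) = 0.009.

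**The case against.** The strongest reply is that little is at stake. The endpoint is exploratory and does not appear among the synopsis objectives. It is summarised descriptively with 8 women per active arm, and no test or decision rests on it. The placebo comparisons in Section 11.3.3 are specified for the hormones. A safety visit two weeks after dosing is ordinary practice. All of this stands and sets the rating.

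It is also fair to say that Table 9-1 is the complete schedule and that two weeks in Section 6 may be a round figure. The limit of 34-37 days from the table is therefore the firmer one, and 33 days arises only on an exact reading of Section 6.

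Three stronger readings are tempting and are not supported:
- A reader might take 2.4-3.9 days instead of 5 as the bias. That range compares raw Cycle 2 lengths and matches the change endpoint only if a woman's two cycles are uncorrelated. Entry requires regular periods, so some correlation is plausible and the shortfall is then smaller.
- A reader might infer that the planned analysis is biased. Section 11.3 says only that summaries rest primarily on non-missing values and refers the detail to the RAP, which may treat open cycles as censored.
- A reader might infer that the effect will be too large to estimate. With a 10-day extension 55-84% of cycles would be open even at Day 38, and the median could not be reached. But Section 4.1 gives no number of days, so nothing in the protocol points to an effect of that size.

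Sites could telephone, since Section 12 counts a call as contact when defining the end of the study. Nothing requires a call for this date.

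**Conclusion.** The point holds as a minor one. The protocol stops collecting the end of Cycle 2 at the follow-up visit, which limits recorded lengths to 34-37 days (33-34 on the exact reading of Section 6). That follows from the protocol's own days.

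The size of the consequence rests on assumed cycle-length parameters. For a 5-day extension, between about a quarter and somewhat over half of cycles would be open at Day 35, and at most about a quarter at Day 38. The difference in change from baseline seen in recorded cycles would be about 2.4-4.7 days or 3.5-4.9 days respectively, over correlations of 0 to 0.7. With a short extension and a Day 38 visit the problem nearly disappears. The primary hormone endpoints and the Cohort 2 decision, which rests on estradiol, are unaffected.

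**What to change.** Keep the follow-up visit as it is for safety. For any woman whose menses have not started by then, obtain the onset date by telephone or diary until menses or 30 days after the last dose (Day 50/51), whichever comes first. That period is already in use for serious adverse events (Section 9.2.5), contraception (Section 8.8.2) and pregnancy reporting (Section 10.2). Give the same follow-up window in Section 6 and Table 9-1, in days after the last dose. How cycles still open at the limit are analysed can stay with the RAP.

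The cost is a few contacts, a line in Section 6 and one in Table 9-1, and a later last contact for some women. No extra clinic visits, samples or subjects are needed, and the end-of-study definition in Section 12 can stand.
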